3.2 Exclusion Criteria

The following attributes will render a participant ineligible for this study:

- 3.2.1 Participants must not have had chemotherapy within the past 10 days.
- 3.2.2 Participants must not have had prior treatment with an EGFR kinase inhibitor, EGFR directed therapy or investigational agent.
- 3.2.3 Participants must not have residual adverse events from previous therapy greater than CTCAE v4.0 grade 2 at the time of registration.
- 3.2.4 Participants must not have symptomatic brain metastases or brain metastases requiring steroids. Asymptomatic brain metastases not requiring steroids are acceptable.
- 3.2.5 Participant must not have a history of allergy to erlotinib.
- 3.2.6 Second primary cancer which is active and requiring treatment.
- 3.2.7 Participants must not be known to be pregnant or breastfeeding.

CONFIDENTIAL

3.3 Inclusion of Women, Minorities and Other Underrepresented Populations

Participants who are enrolled on study will reflect the patient population seen at the Dana Farber/Harvard Cancer Center. This study is designed to be enriched for patients who are more likely to possess an *EGFR* mutation. As a result, participants of Asian race will be preferentially enrolled in this study. This study does not exclude participants of other ethnicities.

4. **REGISTRATION PROCEDURES**

4.1 General Guidelines for DF/HCC Institutions

Institutions will register eligible participants in the Clinical Trials Management System (CTMS) OnCore. Registrations must occur prior to the initiation of protocol therapy. Any participant not registered to the protocol before protocol therapy begins will be considered ineligible and registration will be denied.

An investigator will confirm eligibility criteria and a member of the study team will complete the protocol-specific eligibility checklist.

Registration on the Initial Registration arm (Step 1) occurs at the time of initial plasma genotyping. Registration to the erlotinib treatment arm (Step 2) takes place once positive EGFR mutation status is confirmed. Following registration for erlotinib treatment, participants may begin protocol therapy. Issues that would cause treatment delays should be discussed with the Overall Principal Investigator (PI). If a participant does not receive protocol therapy following registration, the participant's registration on the study must be canceled. Registration cancellations must be made in OnCore as soon as possible.

4.2 Registration Process for DF/HCC Institutions

DF/HCC Standard Operating Procedure for Human Subject Research Titled *Subject Protocol Registration* (SOP #: REGIST-101) must be followed.

4.3 General Guidelines for Other Participating Institutions

N/A

4.4 Registration Process for Other Participating Institutions

N/A

5. STUDY PROCEDURES

5.1 Initial Plasma Genotyping

All participants will undergo a paired blood draw on the same day that they are registered in the study. Blood may be drawn the following business day if same day draw is not feasible. Three 10 mL EDTA tubes of blood will be collected at the clinical blood lab. Plasma will be prepared immediately after the blood draw, frozen and one tube transported to the central laboratory at the Brigham & Women's Hospital Center for Advanced Molecular Diagnostics (CAMD) and the two remaining tubes transported to the CONFIDENTIAL

translational research lab (TRL) at DFCI for exploratory studies (Appendix A: Plasma Preparation SOP). Extraction of cfDNA and ddPCR-based plasma genotyping for *EGFR* exon 19 del, L858R and T790M mutations will then be performed at CAMD as previously described.¹² The remaining plasma shipped to the TRL will be used for confirmatory *EGFR* plasma genotyping, *KRAS* G12X plasma genotyping and exploratory studies (9. Correlative/Special Studies). Participants with positive or pending plasma genotyping on study.

5.2 Serial Plasma Genotyping

Participants which are found to have a detectable *EGFR* exon 19 del or L858R mutation on initial plasma genotyping will subsequently undergo serial plasma genotyping. A single 10 mL EDTA tube of blood will be drawn on Cycle 1 Day 1 and at set intervals of 2 weeks, 6 weeks, 12 weeks, 18 weeks, 24 weeks and approximately every 2-3 months on therapy. A final sample for plasma genotyping will be collected on study termination if not coinciding with one of the previous timepoints. Blood samples will be collected in the clinical blood lab and plasma prepared immediately after the blood draw, frozen and transported to the central laboratory at CAMD (Appendix A: Plasma Preparation SOP). Extraction of cfDNA and ddPCR-based plasma genotyping for *EGFR* exon 19 del, L858R, T790M and *KRAS* G12X mutations will be performed. Unused plasma and cfDNA will be stored and utilized for exploratory studies (9. Correlative/Special Studies).

5.3 Tissue Genotyping

All participants should undergo initial tissue genotyping on available biopsy material as per institutional standard of care at the site at which they are enrolled in the study. If available, this genotyping must be pending or ordered at the time of enrollment and must include at least testing for *EGFR* mutations and *ALK* rearrangements. If not available, a plan to obtain this tissue through biopsy must exist. If biopsy fails or is not technically feasible, patients with detectable *EGFR* mutation by plasma genotyping may still receive erlotinib on the treatment phase of the study. Targeted next-generation gene sequencing (NGS) will be requested for each patient where sufficient tissue is available but will not be a requirement for enrollment in the study. Given that tissue genotyping for *EGFR* and *ALK* are considered standard of care, the cost of these tests will not be covered by the study. Should a patient have insufficient tissue for genotyping as a part of standard of care will be left to the individual investigator based on their standard practice.

For patients that are *EGFR* mutation positive and are treated with erlotinib, re-biopsy and repeat genotyping for resistance mutations will be encouraged at the time of disease progression. The results from this testing will be collected by the study where available in order to examine rates and mechanisms of acquired resistance to erlotinib. Any biopsy done to determine tumor genotype will be considered standard of care and will not be reimbursed by the study.

6. TREATMENT PLAN

Participants found to possess an *EGFR* exon 19 del or L858R mutation on rapid plasma genotyping will begin treatment with erlotinib. Erlotinib is an oral tyrosine kinase inhibitor which is approved for the treatment of advanced EGFR mutant NSCLC. Erlotinib will be initially dosed at 150 mg daily and will be given on a 6-week cycle with treatment administered on an outpatient basis. Dose reductions will be performed in response to expected toxicities of treatment (7. Expected Toxicities and Dosing Delays/Modifications). No other concurrent anti-neoplastic systemic therapies may be prescribed while the patient is participating in the study.

Treatment Description						
Agent	AgentPre-medicationsDoseRouteScheduleCycle Length					
Erlotinib	None	150 mg	ро	Daily for 6 weeks (42 days)	Every 6 weeks (42 days)	

6.1 **Pre-treatment Criteria**

6.1.1 Cycle 1, Day 1

All study participants must meet eligibility requirements in order to enroll in the study and undergo initial plasma genotyping. Those participants found to possess an *EGFR* exon 19 del or L858R mutation on plasma genotyping will be treated with erlotinib. *EGFR* negative patients by plasma ddPCR will not be treated on study but will be followed on the study until they begin standard of care therapy. All participants must have been assessed by an oncology provider within 4 weeks of registration with a history, physical examination, CBC, serum chemistry and liver function tests. Baseline staging investigations including a CT chest/abdomen with bone scan or PET/CT must be performed within 1 month of starting treatment. Either an MRI brain or CT head with contrast is also required within 1 month of starting treatment. Subjects must meet the following criteria to begin treatment:

- ECOG performance status of 0-2
- Platelets >75
- AST & ALT < 3x the upper limit of normal
- Creatinine clearance > 30 mL/min by Cockroft-Gault
- No other contraindication to erlotinib
- Female participants of child-bearing age must agree to use adequate contraception (hormonal, barrier or abstinence) for the duration of the study while receiving erlotinib and undergo a pregnancy test. Any evidence or suspicion of pregnancy should be reported to the treating physician immediately.
- Male participants must agree to use adequate contraception for the duration of the study while receiving erlotinib

6.1.2 Subsequent Cycles

During subsequent cycles, treatment dosing should be performed according to the dose modifications details in Section 7.3.

6.2 Agent Administration & Storage

6.2.1 Erlotinib

Erlotinib will be administered orally on a continuous schedule with a dose of 150 mg po daily on a 6 week cycle of treatment. The beginning of any cycle of treatment may be delayed at the clinical provider's discretion for the treatment of therapy-related toxicities. Dose modification at the beginning of any cycle may be performed due to toxicity as described (7. Expected Toxicities and Dosing Delays/Modifications). If participants neglect to take a dose, they will be instructed to take the dose if there is more than 12 hours until the next dose. If a dose is vomited within 30 minutes of taking it, the participant will be instructed to utilize an anti-emetic and repeat the dose. Tablets should not be crushed, split, or dissolved in water.

Erlotinib tablets will be provided by the study at the appropriate dosage in 6 week cycles with overage. The tablets should be stored at room temperature. No pre-medication is required for treatment.

6.3 Definition of Dose-Limiting Toxicity

N/A

6.4 General Concomitant Medication and Supportive Care Guidelines

Participants should receive all appropriate supportive care at the discretion of their primary oncologist (e.g. topical steroids, antibiotics, anti-emetics, g-csf, transfusions). Concomitant use of full-dose anticoagulation using low-molecular weight heparin or other indicated anticoagulation is permitted with the exception of warfarin (see below). Treatment of skin toxicities including topical corticosteroids and topical/oral antibiotics is encouraged. The use of oral corticosteroids is discouraged for skin toxicity \leq grade 2 but may be used at the discretion of the oncologist. Use of corticosteroids to treat brain metastases is prohibited at study entry.

In addition, the following concomitant therapies are discouraged from the study due to known interactions:

- Grapefruit juice (CYP3A4 inhibitor which may increase erlotinib levels and increased toxicity)
- Ciprofloxacin (CYP3A4 and CYP1A2 inhibitor which may increase erlotinib levels and increased toxicity)
- Cigarette smoking should be actively discouraged and all appropriate cessation methods employed. Smoking may induce CYP1A2 and result in lowered erlotinib levels and thus decreased effectiveness.
- Other significant CYP3A4 inhibitors or inducers (Appendix D)
- Other anti-neoplastic systemic therapies
- Warfarin

The absorption of erlotinib may also be dependent on gastric pH and thus the use of proton pump inhibitors (PPI) such as omeprazole should be limited as it may decrease the bioavailability of the drug. However, the use of PPIs is not explicitly excluded but if medically necessary should be maximally separated from the erlotinib dose although this may still result in reduced bioavailability. Additional potential drug-drug interactions should be reviewed by the enrolling sub-investigator as per standard of care and medications discontinued as appropriate (please refer to erlotinib FDA package insert for full list of potential drug-drug interactions).

6.5 **Duration of Therapy**

Participants with an *EGFR* sensitizing mutation by plasma ddPCR will receive erlotinib 150 mg daily without interruption. No maximum number of cycles of treatment is prescribed in this study. However, treatment dose may be decreased or interrupted secondary to toxicity as described (7. Expected Toxicities and Dosing Delays/Modifications). Duration of therapy will depend on individual response, evidence of disease progression and tolerance. In the absence of treatment delays due to adverse events, treatment may continue until one of the following criteria applies:

- Disease progression warranting treatment change (investigator determined),
- Unacceptable adverse event(s) defined as \geq grade 3 toxicity that does not resolve with dose reduction or holding treatment.

CONFIDENTIAL

• Participant demonstrates an inability or unwillingness to comply with the oral medication regimen and/or documentation requirements

- Participant decides to withdraw from the study, or
- General or specific changes in the participant's condition render the participant unacceptable for further treatment in the opinion of the treating investigator.

Subjects who, at time of radiographic progression, are deemed to be gaining clinical benefit from erlotinib in the opinion of the treating investigator may continue treatment with erlotinib on study. Objective progression will not be a pre-defined endpoint of this study and will not be measured centrally in this study. As previously described, objective response rate will be the primary study endpoint and will be assessed by central radiologists per RECIST v1.1.

Additionally, patients with progression in the brain only while on treatment and without evidence of systemic progression can, after completion of local therapy to the brain (e.g. radiation therapy) continue treatment with erlotinib on protocol. For these patients, criteria for objective progression will have been met for the purposes of calculation of progression free survival, but treatment with erlotinib can continue until systemic progression or intolerable toxicity at the judgment of the treating investigator. Study drug should be held on days when radiation therapy is given; additional washout before or after radiation is at the discretion of the investigator.

6.6 Treatment Assessments

As described, all participants will undergo initial screening with plasma genotyping. They will undergo assessment of eligibility at the same clinic visit and appropriate examinations/testing/baseline staging will be performed as described (6.1. Pre-Treatment Criteria).

On Treatment Assessments: Participants treated with erlotinib will be evaluated by an oncology provider every cycle (6 weeks) with a routine history and physical. Bloodwork including at least a CBC, chemistry and LFTs must be performed within a week of each assessment. CT scanning of all sites of disease will be performed every 6 weeks for the first 24 weeks and then at least every 3 months thereafter unless otherwise clinically indicated. Patients positive for an *EGFR* mutation by plasma genotyping but negative by tissue genotyping will undergo an interim CT scan at 4 weeks after initiating erlotinib to confirm response. Serial plasma genotyping will be performed at 2 weeks after starting treatment and then with every re-staging CT scan. After the fourth CT scan, clinical visits and blood work may be relaxed to every 12 weeks coinciding with imaging investigations.

End of Study Assessments: Participants will be treated with erlotinib until evidence of significant disease progression or unacceptable toxicity. A final blood draw for plasma genotyping will be performed at the time of study termination for each participant.

6.7 Duration of Follow Up

Participants will be followed within 28 days (+/- 7 days) of their last dose of erlotinib for possible treatment-related adverse events. Participants removed from study for unacceptable treatment-related adverse events will be followed until resolution or stabilization of the adverse event.

6.8 Criteria for Removal from Study

Participants positive for an *EGFR* sensitizing mutation by plasma ddPCR will be removed from study when any of the criteria listed in Section 6.5 applies. *EGFR* negative patients by plasma ddPCR will be removed

from the study when they begin standard of care therapy. The reason for study removal and the date the participant was removed must be documented in the study-specific case report form (CRF). Alternative care options will be discussed with the participant.

In the event of unusual or life-threatening complications, participating investigators must immediately notify the Principal Investigator (or Protocol Chair), [name] at [contact].

7. EXPECTED TOXICITIES AND DOSING DELAYS/DOSE MODIFICATIONS

Dose delays and modifications will be made using the following recommendations. Toxicity assessments will be done using the CTEP Active Version of the NCI Common Terminology Criteria for Adverse Events (CTCAE version 4.0) which is identified and located on the CTEP website at: http://ctep.cancer.gov/protocolDevelopment/electronic_applications/ctc.htm.

If possible, symptoms should be managed symptomatically. In the case of toxicity, appropriate medical treatment should be used (including anti-emetics, anti-diarrheals, etc.).

All serious adverse events (CTCAE v4.0 Grade \geq 3) experienced by participants will be collected from the time of the first dose of study treatment, through the study and until the final study visit. Participants continuing to experience toxicity at the off study visit may be contacted for additional assessments until the toxicity has resolved or is deemed irreversible.

7.1 Anticipated Toxicities

Erlotinib is an approved drug for the treatment of *EGFR* mutant advanced NSCLC. As such, appropriate measures will be taken to ensure the safety of participants in this study in accordance with current standards of care. Toxicity will be assessed by individual study investigators for each patient at their regular clinic visits or more frequently if clinically indicated. Investigators will manage all toxicity as per standard care but will only be required to report related grade 3 or greater toxicity.

Common toxicities of erlotinib include: -diarrhea -acneiform rash -skin/hair/nail changes

Rare but concerning toxicities include: -interstitial lung disease -transaminitis/hepatotoxicity -renal failure -gastrointestinal perforation -bullous and exfoliative skin disorders including Stevens-Johnson syndrome/toxic epidermal necrolysis -myocardial infarction/ischemia -cerebrovascular accident -microangiopathic hemolytic anemia with thrombocytopenia -ocular disorders including corneal ulceration/perforation -embryofetal lethality/severe fetal harm

Please refer to erlotinib FDA package insert for additional details on frequency of these toxicities.

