7.3 Dose Modifications/Delays

For subjects receiving erlotinib, dose interruptions or reductions may be required following potential drug-related toxicities. Rash, diarrhea, pneumonitis, hepatotoxicity and other adverse events have been reported in response to treatment with erlotinib. Toxicity-related dose reduction is permitted at the discretion of the treating investigator. Dose reduction is recommended if two toxicity-related dose interruptions are required. Dose interruption of more than 14 consecutive days will result in a patient coming off study.

At each visit during the Treatment Period, subjects should first be evaluated for the occurrence of adverse events and laboratory abnormalities. Management of possible adverse events as well as dose delay/modification or discontinuation of study treatment should occur as per institutional standard of care for erlotinib. Specific treatment of these toxicities will be decided by the treating oncologist for each patient. Adverse events are graded according to NCI Common Terminology Criteria for Adverse Events v4.0. However, only grade 3 and greater toxicities will be reported in this study given the erlotinib is already an FDA approved drug for the treatment of NSCLC.

If dose reduction is necessary, two possible dose reductions are suggested in a stepwise fashion (initially to 100 mg and subsequently to 50mg if necessary). Decisions regarding dose reduction will be made by the treating oncologist and dose reductions encouraged particularly in elderly patients or those with treatment-related toxicity. Dose escalation after dose reduction is not permitted.

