12.1.2 Serious adverse event (SAE)

A serious adverse event (SAE) is any adverse event, occurring at any dose and regardless of causality that:

• Results in death

• Is life-threatening. Life-threatening means that the person was at immediate risk of death from the reaction as it occurred, i.e., it does not include a reaction which hypothetically might have caused death had it occurred in a more severe form.

• Requires or prolongs inpatient hospitalization (i.e., the event required at least a 24-hour hospitalization or prolonged a hospitalization beyond the expected length of stay). Hospitalization admissions and/or surgical operations scheduled to occur during the study period, but planned prior to study entry are not considered SAEs if the illness or disease existed before the person was enrolled in the trial, provided that it did not deteriorate in an unexpected manner during the trial (e.g., surgery performed earlier than planned).

• Results in persistent or significant disability/incapacity. Disability is defined as a substantial disruption of a person's ability to conduct normal life functions.

• Is a congenital anomaly or birth defect; or

• Is an important medical event when, based upon appropriate medical judgment, it may jeopardize the participant and require medical or surgical intervention to prevent one of the outcomes listed above. Examples of such medical events include allergic bronchospasm requiring intensive treatment in an emergency room or at home; blood dyscrasias or convulsions that do not result in inpatient hospitalization, or the development of drug dependency or drug abuse.

Events **not** considered to be serious adverse events are hospitalizations for:

- routine treatment or monitoring of the studied indication, not associated with any deterioration in condition, or for elective procedures
- elective or pre-planned treatment for a pre-existing condition that did not worsen
- emergency outpatient treatment for an event not fulfilling the serious criteria outlined above and not resulting in inpatient admission
- respite care

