12.2 Procedures for AE and SAE Recording and Reporting

Participating investigators will assess the occurrence of CTCAE v4.0 grade \geq 3 AEs and SAEs at all participant evaluation time points during the study.

All CTCAE v4.0 grade \geq 3 AEs and SAEs whether reported by the participant, discovered during questioning, directly observed, or detected by physical examination, laboratory test or other means, will be recorded in the participant's medical record and on the appropriate study-specific case report forms.

The descriptions and grading scales found in the revised NCI Common Terminology Criteria for Adverse Events (CTCAE) version 4.0 will be utilized for AE reporting. All appropriate treatment areas should have access to a copy of the CTCAE version 4.0.

A copy of the CTCAE version 4.0 can be downloaded from the CTEP website at:

http://ctep.cancer.gov/protocolDevelopment/electronic_applications/ctc.htm.

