12.4.2 Non-Serious Adverse Event Reporting

Non-serious grade 3 or greater adverse events will be reported to the DF/HCC Overall Principal Investigator on the toxicity Case Report Forms. Given that erlotinib is an FDA approved medication for the treatment of advanced NSCLC, adverse events of grade 2 or less should be recorded in the patient's medical record as a part of standard of care but do not need to be reported centrally to the trial.

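### Sections 7, 7.1 and 7.3 set a narrower adverse event reporting rule than section 12, so non-serious grade 3+ events judged unrelated could go unreported and low-grade SAEs could be misread as not reportable

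*Combined protocol and SAP*

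**What the plan says.** Three places in section 7 set a reporting or collection scope.

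- The opening of section 7 speaks of "All serious adverse events (CTCAE v4.0 Grade" ≥ 3), which treats seriousness and severity grade as the same thing.
- Section 7.1 states that investigators "will only be required to report related grade 3 or greater toxicity".
- Section 7.3 states that "only grade 3 and greater toxicities will be reported in this study", with no mention of relatedness.

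Section 12 sets a different scope.

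- Section 12.1.2: "A serious adverse event (SAE) is any adverse event, occurring at any dose and regardless of causality that" meets one of a list of outcomes such as death, hospitalization or disability. No grade appears in the definition.
- Section 12.2 covers all events of CTCAE grade ≥ "3 AEs and SAEs whether reported by the participant, discovered during questioning, directly observed, or detected by physical examination" or by other means. These "will be recorded in the participant's medical record and on the appropriate study-specific case report forms". There is no relatedness condition.
- Section 12.4.1 sends all SAEs, from first dose to 30 days after the last, to the overall principal investigator.
- Section 12.4.2: "Non-serious grade 3 or greater adverse events will be reported to the DF/HCC Overall Principal Investigator", again with no relatedness condition.

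**The concern.** The two sections give a site different instructions for the same event. Section 7.1 filters on the investigator's view of causality; section 12 does not. Sections 7 and 7.3 use a grade threshold where section 12 also uses an outcome-based definition of seriousness.

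What is at stake is the completeness of the toxicity data. The study has one open-label arm, so there is no control group against which to check attribution judgements. Events dropped because they were called unrelated cannot be reassessed later if they were never reported. Section 13.2 has the data and safety monitoring committee review toxicity. If sites work from different sections, what the committee sees would depend partly on which section each site read.

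**Working it through.** The plan states no figure on this point, so there is nothing to reproduce. The check is to take each class of event and ask what each section requires.

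| Event | Section 7 (opening, 7.1, 7.3) | Section 12 | Agree? |
|---|---|---|---|
| Grade 3+, non-serious, judged related | Reportable under 7.1 and 7.3; the opening would label it serious | CRF (12.2) and central report as non-serious (12.4.2) | On reporting, yes; on the label, no |
| Grade 3+, non-serious, judged unrelated | Not required by 7.1; covered by 7.3 unless toxicity is taken to mean drug-related | CRF (12.2) and central report (12.4.2) | No |
| Grade 3+, meets an SAE outcome, judged unrelated | Not required by 7.1; collected under the opening | 12.2, 12.4.1, 12.5, 12.10 | No for 7.1, but section 12 requires it in four places |
| Grade 1-2, meets an SAE outcome | Outside all three statements | 12.2, 12.4.1, 12.5, 12.10 | No, but section 12 requires it in four places |
| Grade 1-2, non-serious | Not reported | Medical record only (12.4.2) | Yes |

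Three readings that might remove the conflict were tried.

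1. *Section 7.1 concerns reporting and 12.2 concerns recording, so both can hold.* This fails at 12.4.2, which is itself a reporting rule, covers non-serious grade 3+ events, and has no relatedness condition.
2. *Section 7.1 restates the grade 3 item in 12.4.1, which is limited to unexpected events that are at least possibly related.* That item is listed in addition to events meeting the SAE criteria. It widens what goes on the SAE form and does not narrow the general duty in 12.2 and 12.4.2.
3. *The parenthesis in section 7 is a definition of serious.* Then the non-serious grade 3+ category in 12.4.2 would be empty, and 12.1.2 would be contradicted.

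Section 7 also disagrees with itself: 7.1 carries the relatedness filter and 7.3 does not. Section 7.1 does not say which of the five attribution levels in 12.1.4 count as related.

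On size, an under-count would need the all-cause grade 3+ rate, the share judged unrelated, the share of those that are non-serious, and the share of sites following section 7. The documents give none of these, so no estimate is offered.

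**The case against.** The strongest reply is that section 12 is the chapter on adverse event reporting, while section 7 is about expected toxicities and dose changes, so section 12 should be taken to govern. For SAEs this largely stands. Section 12.3 tells investigators to report them as that section goes on to describe; 12.2, 12.4.1, 12.5 and 12.10 each require them, and 12.10 does so irrespective of relatedness. Losing a grade 2 hospitalization would mean overlooking all of these. There are other safeguards too: the study calendar schedules assessment of high-grade events at treatment visits with no causality filter, and section 13.3 has monitors verify safety events for all enrolled participants.

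It does not dispose of the point for non-serious grade 3+ events judged unrelated. There the safeguards are 12.2 and 12.4.2, which 7.1 contradicts directly, and no general rule says which prevails. Section 12's own pointers do not help: 12.4.1 refers to section 11.1.2 for the SAE criteria, which is the section on disease parameters, and 12.1.3.1 refers to section 6.1 for expected events, which is the pre-treatment criteria.

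A reader might infer more than this: that unrelated or low-grade SAEs will be lost, or that the reported toxicity rate will be materially too low. The documents support neither. Section 12 requires those SAEs independently, and any figure for the shortfall would rest on invented rates and on every site disregarding section 12.

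It is also fair to say that no planned inference changes. Section 15 contains no toxicity endpoint, threshold or stopping rule, and the documents describe erlotinib as an approved drug at its standard starting dose.

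**Conclusion.** The inconsistency is real and is in the current text. Its main exposure is narrow: non-serious grade 3+ events that the investigator judges unrelated, which 7.1 excuses and 12.2 and 12.4.2 require. A secondary exposure is that a grade 1-2 SAE could be taken as not reportable from sections 7, 7.1 and 7.3, although section 12 separately requires it.

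Under-counting is possible, not certain. It depends on a site following section 7; a site that follows section 12 captures everything. Its size cannot be derived from the documents. The response-rate endpoint and its decision rule are untouched. This is a conflict of wording, not a flaw in the design, since collecting all grade 3+ events and all SAEs is already what section 12 provides for. It is worth correcting because the safety committee relies on these data and the correction costs very little.

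**What to change.** In sections 7, 7.1 and 7.3, replace the reporting and collection wording with one common sentence:

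*All grade 3 or greater adverse events regardless of attribution, and all SAEs of any grade as defined in 12.1.2, will be recorded and reported as described in section 12.*

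All three places need the change. Amending 7.1 alone would leave the grade-only statement in 7.3 in conflict with reporting a low-grade SAE, and a version of 7.1 that named only grade 3+ events would still omit SAEs of lower grade.

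The cost is a protocol wording amendment and a few more case report form entries at sites that had followed 7.1. Section 12 already requires those data, so no visit, test or participant is added.
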